7.4 Reporting Procedures for Serious Adverse Events/Reactions (SAE/R)

The Sponsor, the CI or the local PI at a research site may take appropriate urgent safety measures in order to protect research participants against any immediate hazard to their health or safety. If any urgent safety measures are taken, the CI/Sponsor shall be notified immediately, and in any event no later than 3 days from the date the measures are taken, give written notice to the Sponsor and the relevant REC of: the measures taken; reason these measures were taken; the circumstances giving rise to those measures and the plan for further actions.

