7.1 Definitions

SPONSOR REFERENCE: 1097

OurPERSPECTIVE endometrial cancer survivorship Study

Protocol Version v1.0 14/10/2025

IRAS: 363748

Term	Definition
Adverse Event (AE)	Any untoward and unintended medical occurrence (including an abnormal laboratory finding), symptom or disease in a participant, whether or not it is considered related to the study.
Adverse Reaction (AR)	
Any untoward and unintended medical occurrence (including an abnormal laboratory finding), symptom or disease in a participant which is considered related to the study.
 
The assessment of expectedness must be undertaken by a delegated medically qualified professional.
 
Where an event could be considered possibly, probably or unlikely related to the study, for the avoidance of doubt, this should be considered related.

Serious Adverse Event (SAE)	
Any untoward and unintended medical occurrence that meets the following serious criteria, whether or not it is considered related to the study:
 
 • results in death • is life-threatening[^] • requires inpatient* hospitalisation or prolongation of existing hospitalisation • results in persistent or significant disability/incapacity, or • is a congenital anomaly/birth defect • Other 'important medical events' may also be considered serious if they jeopardise the participant or require an intervention to prevent one of the above consequences. 
NOTE:
 
[^]The term "life-threatening" in the definition of "serious" refers to an event in which the participant was at risk of death at the time of the event; it does not refer to an event which hypothetically might have caused death if it were more severe.

Serious Adverse Reaction (SAR)	Any untoward and unintended medical occurrence that meets the above referenced serious criteria and, in the opinion of the delegated medically qualified professional, is believed to be related (possibly, probably, unlikely) to the study intervention.

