Suspected Unexpected Serious Adverse Reaction (SUSAR)	
Any untoward and unintended medical occurrence that meets the above referenced serious criteria and, in the opinion of the delegated medically qualified professional, is believed to be related to the study intervention but is not listed within the anticipated events section below.
 
Any untoward and unintended medical occurrence that meets the above referenced serious criteria and, in the opinion of the delegated medically qualified professional, is believed to be related to the study intervention. There are no anticipated

SPONSOR REFERENCE: 1097

OurPERSPECTIVE endometrial cancer survivorship Study

Protocol Version v1.0 14/10/2025

IRAS: 363748

	events for this study therefore, any events which are considered related will be considered unexpected.
--	--

NB: to avoid confusion or misunderstanding of the difference between the terms “serious” and “severe”, the following note of clarification is provided: “Severe” is often used to describe intensity of a specific event, which may be of relatively minor medical significance. “Seriousness” is the regulatory definition supplied above.

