7.2.2 Expected Serious Adverse Events

There are no anticipated SAEs in the population being studied.

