7.3 Reporting procedures for All Adverse Events/Reactions

All non-serious Adverse Events/Adverse Reactions occurring from the time of start of study intervention until the end of the participants involvement in the study, observed by the investigator or reported by the participant, will be recorded.

The following information will be captured on the adverse event log;

- Description of the event
- Date of onset
- End date
- Severity*
- Assessment of relatedness to study (not related or related; possibly, probably unlikely)
- Action taken

Follow-up information will be provided as necessary.

The relationship of the event to the study will be assessed and signed off by a medically qualified individual listed on the Delegation of Authority and Signature Log.

Events will be followed-up until resolution or the event is considered stable.

It will be left to the investigator's clinical judgment whether or not an AE is of sufficient severity to require the participant's removal from the study (or the study intervention/procedures). A participant may also voluntarily withdraw from treatment/the study due to what he or she perceives as an intolerable AE. If either of these occurs, the participant must undergo an end of study assessment and be given appropriate care under medical supervision until symptoms cease or the condition becomes stable.

SPONSOR REFERENCE: 1097

OurPERSPECTIVE endometrial cancer survivorship Study

Protocol Version v1.0 14/10/2025

IRAS: 363748

*The severity of events will be assessed on the following scale: 1 = mild, 2 = moderate, 3 = severe.

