7.5 Reporting Urgent Safety Measures

The Sponsor, the CI or the local PI at a research site may take appropriate urgent safety measures in order to protect research participants against any immediate hazard to their health or safety. If any urgent safety measures are taken, the CI/Sponsor shall be notified immediately, and in any event no later than 3 days from the date the measures are taken. Written notice must be provided to the Sponsor and the relevant REC of:

- the measures taken
- reason these measures were taken
- the circumstances giving rise to those measures
- plan for further actions.

8 Statistics and Analysis

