11.1 Protocol deviations

A study related deviation is a departure from the ethically approved study protocol or other study document or process (e.g. consent process or administration of study intervention) or from Good Clinical Practice (GCP) or any applicable regulatory requirements. Planned deviations or waivers are not allowed however it is acknowledged that accidental protocol deviations may occur. Any deviations from the protocol will be documented in a protocol deviation form and filed in the Trial Master File/Investigator Site File as applicable.

If a protocol deviation occurs, then the CI (or delegate) will document this in accordance with the University’s Standard Operational Procedure (SOP) Identifying and Reporting Deviations and Serious Breaches of GCP and/or the Protocol.

Deviations from the protocol which are found to frequently recur will be explored and where necessary an amendment to the protocol will be made.

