11.2 Serious breaches

A “serious breach” is a breach of the protocol or of the conditions or principles of Good Clinical Practice which is likely to affect to a significant degree –

- (a) the safety or physical or mental integrity of the trial subjects; or
- (b) the scientific value of the research.

In the event that a serious breach is suspected the Sponsor will be contacted within one working day. In collaboration with the CI, the serious breach will be reviewed by the Sponsor and, if appropriate, the Sponsor will report it to the approving REC committee and the relevant NHS host organisation within seven calendar days.

12 Ethical and Regulatory Considerations

12.1 Research ethics committee (REC) and regulatory review, approvals/permission/support, compliance and reports

Once the Sponsor Review process is complete, authorisation from the University of Leicester’s Research Governance Office will be issued to book further regulatory review of the proposed research. The University of Leicester’s Ethics Committee will then review the proposal. Agreement in principle is subject to the research receiving all relevant regulatory permissions. Submission for regulatory approvals will occur via the Integrated Research Application System (IRAS). The Chief Investigator will ensure that all regulatory approvals,

SPONSOR REFERENCE: 1097

OurPERSPECTIVE endometrial cancer survivorship Study

Protocol Version v1.0 14/10/2025

IRAS: 363748

confirmation of capacity and capability from NHS sites and sponsor green light are in place before participants are approached.

For any required amendment(s) to the study, amendment will be submitted to the sponsor in the first instance for review and approval to submit the amendment for external regulatory approval. Amendments must be implemented following all required ethical, competent authority, site and Sponsor approvals and in line with Sponsor Standard Operating Procedures.

The Research Governance Office's Standard Operating Procedures will be followed for the duration of the study.

The Chief Investigator will notify the REC when the study has ended by completing the end of study notification form and will submit a final report of the results within one year after notifying REC.

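### Section 7.4, headed as the SAE/R reporting procedure, contains only urgent-safety-measures text; as 7.3 records only non-serious events, the protocol states no procedure for serious ones.

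*Protocol*

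**What the plan says.** **Definitions (7.1 and 7.2).** Section 7.1 defines SAE, SAR and SUSAR. An SAE counts whether or not it is related to the study, and inpatient hospitalisation is one of the criteria. A SAR is a serious event that, "in the opinion of the delegated medically qualified professional, is believed to be related (possibly, probably, unlikely) to the study intervention". The SUSAR row says that, with nothing anticipated, "any events which are considered related will be considered unexpected". Section 7.2.2 agrees: "There are no anticipated SAEs in the population being studied".

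**Section 7.3.** The heading covers all adverse events and reactions, but the recording rule begins "All non-serious Adverse Events/Adverse Reactions occurring from the time of start of study intervention". It then lists what goes on the adverse event log.

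**Section 7.4.** The heading is the SAE/R reporting procedure. The text says who may take urgent safety measures, that the CI/Sponsor is to be told, and that someone must, "no later than 3 days from the date the measures are taken, give written notice to the Sponsor and the relevant REC of", the measures, the reason, the circumstances and the further plan.

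**Section 7.5.** The heading is urgent safety measures. The content is the same with slightly different wording ("Written notice must be provided to the Sponsor and the relevant REC of") and the four items set as bullets.

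**Elsewhere.** Section 12.1 says in general terms that the Research Governance Office's SOPs apply throughout the study. Section 11.2 sets a time limit for a different matter: "In the event that a serious breach is suspected the Sponsor will be contacted within one working day".

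**The concern.** The three reporting sections appear to be meant as a set: 7.3 for non-serious events, 7.4 for serious events and 7.5 for urgent measures. With the urgent-measures text standing in both 7.4 and 7.5, the middle part is missing. The restriction to non-serious events in 7.3 makes sense only if 7.4 deals with the rest, and it does not.

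What is at stake is oversight of participant safety, not a statistical result. Women are followed to 12 months, and 5.7 itself foresees recurrence and significant health deterioration, so hospital admissions are plausible. Site staff who open 7.4 after such an event find no instruction on what form to complete, whom to tell or how quickly. The Sponsor and the REC could learn of a serious event late or not at all.

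**Working it through.** No arithmetic applies. The check sets the sections side by side and then looks for any other route.

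**Step 1: what each section covers.**

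| Section | Heading | Events covered by the text | Time limit |
|---|---|---|---|
| 7.3 | All AEs/ARs | Non-serious AEs/ARs only | None |
| 7.4 | SAEs/SARs | Urgent safety measures only | 3 days from the measures |
| 7.5 | Urgent safety measures | Urgent safety measures only | 3 days from the measures |

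Apart from its heading, 7.4 never mentions a serious adverse event, a form, or becoming aware of an event.

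**Step 2: is this an artefact of how the document was read?** No. Sections 7.4 and 7.5 differ in phrasing and layout, both are complete, and neither shows a redaction. The contents list also gives them as two separate sections. The likeliest explanation is a template or pasting error.

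**Step 3: does other text supply the route?**

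- *5.7, withdrawal:* records the type of and reason for withdrawal. It does not reach a woman who stays in.
- *7.3, removal paragraph:* applies when an AE leads to removal or voluntary withdrawal. It asks for an end-of-study assessment and care, not a report to the Sponsor.
- *11.2, serious breaches:* one working day to the Sponsor and, where appropriate, seven calendar days to the REC and host. It concerns breaches of the protocol or GCP, not medical events.
- *Appendix 1, distress protocol:* its title limits it to research focus groups and interviews. Its body is not visible.
- *12.1, SOP clause:* general. It neither describes nor cites an SAE procedure.

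Provisions found that state how an SAE, SAR or SUSAR is recorded or reported: 0.

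**Step 4: a worked case.** A participant is admitted to hospital, continues in the study, and no urgent measure is taken.

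1. Under 7.1 the admission is an SAE.
2. The 7.3 recording rule excludes it, because it is serious.
3. The texts of 7.4 and 7.5 are not triggered, because no urgent measure was taken.
4. The records in 5.7 are not triggered, because she has not withdrawn.
5. If the admission is judged related to the intervention, the SUSAR row of 7.1 makes it unexpected, yet no section says who informs the REC or by when.

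**The case against.** **The sponsor's SOPs may already cover this.** This is the strongest reply. Section 12.1 makes the Research Governance Office's SOPs binding for the whole study, and 10.1 places the study under the Sponsor's risk-based monitoring. Those SOPs are not shown, so a reader who infers that serious events have no route at all goes further than the documents allow. It stands that the protocol neither states nor cites a route, and an SOP would not correct a section whose text does not match its heading.

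**Silence proves little.** One might argue that the protocol names the SOPs it relies on, as in 11.1 ("Identifying and Reporting Deviations and Serious Breaches of GCP and/or the Protocol"), and so has none for SAEs. That inference is weak: 12.1 sends amendments through Sponsor SOPs without naming any.

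**The SUSAR reading.** A reader might infer that every SAE not rated as unrelated is a SUSAR. The documents do not say so. The bracketed ratings stand in the SAR row, and neither SUSAR wording repeats them. The ratings in 7.3 belong to non-serious events and concern relatedness to the study rather than to the intervention. The point does not need this reading.

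**Low risk.** Section 12.4 describes the main risks as psychosocial, and they are handled through debriefs, facilitator support, signposting and a distress protocol. This lowers the likely number and consequence of events, which is a fair reason for modest weight. It does not supply a reporting route when a serious event occurs.

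**Conclusion.** The concern holds as a drafting error. Section 7.4 carries the wrong text, 7.3 excludes serious events, and the protocol neither states nor cites a procedure for recording or reporting them. This is not detail that a protocol normally leaves to a statistical analysis plan.

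The size is modest. No feasibility outcome or planned analysis depends on it, and the study is low-risk, non-CTIMP, single-arm and of about 30 women. No event rate is given or assumed here, so the number of affected events is not estimated. The conclusion rests on the protocol text alone. If a sponsor SAE SOP exists and is followed through 12.1, the practical harm is smaller, but 7.4 would still need correcting.

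**What to change.** 1. Replace the text of 7.4 with an SAE procedure that covers four things:
   - recording every SAE on an SAE form, from the start of the intervention to the end of the woman's involvement;
   - assessment of seriousness, relatedness and expectedness by the medically qualified delegate provided for in 7.1;
   - notification of the Sponsor by the CI or delegate within a fixed time of becoming aware;
   - who reports related and unexpected SAEs to the REC, and by when.
2. Take the notification time from the sponsor's SAE SOP and cite that SOP by name. If there is none, one working day is a reasonable example; 11.2 uses that limit for serious breaches, although that is a different process.
3. Keep urgent safety measures in 7.5 only.
4. Add to 7.3 a cross-reference to 7.4 for serious events.

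The cost is protocol wording, an SAE form completed by staff, and a small amount of reporting work. Participants face no new visit or data item, and no new committee is needed.

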7.5 Reporting Urgent Safety Measures

The Sponsor, the CI or the local PI at a research site may take appropriate urgent safety measures in order to protect research participants against any immediate hazard to their health or safety. If any urgent safety measures are taken, the CI/Sponsor shall be notified immediately, and in any event no later than 3 days from the date the measures are taken. Written notice must be provided to the Sponsor and the relevant REC of:

- the measures taken
- reason these measures were taken
- the circumstances giving rise to those measures
- plan for further actions.

8 Statistics and Analysis

8.1 Sample size calculation

The sample size for this feasibility study is pragmatic and based on the anticipated recruitment rate within University Hospitals of Leicester NHS Trust. Approximately 30 participants will be enrolled.

8.2 Planned recruitment rate

It is anticipated that 100% of the recruitments will be through the University Hospitals of Leicester.

8.3 Statistical analysis plan

8.3.1 Summary of baseline data and flow of patients

Data will be collected from all the participants using the CRFs and baseline questionnaires (EQ-5D-5L, HADS, SF-36).

8.3.2 Primary outcome analysis

SPONSOR REFERENCE: 1097

OurPERSPECTIVE endometrial cancer survivorship Study

Protocol Version v1.0 14/10/2025

IRAS: 363748

Primary outcomes will relate to feasibility, including recruitment, retention, attendance and acceptability of the OurPERSPECTIVE programme.

Data will be collected using study Case Report Forms (CRFs) and participant feedback questionnaires. Descriptive statistics will be undertaken to report:

- the proportion of eligible participants who consent to participate;
- the proportion completing the 8-week programme;
- attendance across the six core sessions and 2 optional sessions; and
- acceptability ratings following each session and at study completion.

Quantitative outcomes will be summarised using frequencies and percentages for categorical data and means, standard deviations, medians and interquartile ranges for continuous data as appropriate. No formal hypothesis testing will be undertaken.

Qualitative data generated from the post-intervention focus group will be analysed using Reflexive Thematic Analysis as described by Braun & Clarke (2006). Audio recordings will be transcribed verbatim, anonymised and imported into suitable, confidential software (Microsoft Teams). Data familiarisation, coding, theme development, and refinement will be undertaken iteratively. Two researchers will code independently and discuss discrepancies to ensure credibility. A reflexive log will be maintained to document analytic decisions. Themes will capture participants' perceptions of programme acceptability, perceived benefits and barriers to participation. These qualitative findings will complement the quantitative data to provide a comprehensive assessment of feasibility and acceptability.

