Objectives	Outcome Measures/Endpoints	Timepoint(s) of evaluation of this outcome measure
Primary Objective, Outcome, Timepoint(s)		

Is the OurPERSPECTIVE course acceptable and useful for women who have completed treatment for endometrial cancer?
	
The primary outcome is the acceptability and feasibility of the OurPERSPECTIVE survivorship course.
 
This will be primarily assessed using:
 
 – Retention rates (proportion of participants completing the 8-week course). – Recruitment rates (proportion of eligible women approached who consent to take part). 
These measures will determine whether the intervention and study procedures are acceptable and feasible.
	
Data will be collected in three stages:
 
Before the trial begins to collect baseline participant data.
 
Participants will be asked to keep a diary of their experiences and views of the course and the different modules
 
At week 4 of the 8-week intervention, representing mid-point data, with short interviews with individuals to assess usability and engagement with the intervention.
 
Follow up period after the 8-week intervention at 3-months, 6-months and 12-months post-intervention.

Secondary Objective(s), Outcome(s), Timepoint(s)		

1. Can we recruit and retain women to take part in the OurPERSPECTIVE course within the NHS?
 
2. Do women complete the questionnaires and give feedback as expected?
 
3. What changes or improvements to the course content or delivery are suggested by participants?
	
Secondary outcomes will focus on exploratory measures to inform the design of the subsequent randomised controlled trial. These include:
 
 – Recruitment feasibility, such as reasons for declining participation and the characteristics of those recruited versus not recruited. – Attendance and engagement (number of sessions attended). – Participant evaluation of the course (questionnaire ratings of usefulness and relevance, and 	
Data will be collected in three stages:
 
Before the trial begins to collect baseline participant data.
 
Participant diaries
 
At week 4 of the 8-week intervention, representing mid-point data, with short interviews with individuals to assess usability and engagement with the intervention.
 
Follow up period after the 8-week intervention at 3-months,

SPONSOR REFERENCE: 1097

OurPERSPECTIVE endometrial cancer survivorship Study

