Attendance at each of the 8 weekly online group sessions will be recorded in the case report form. Sessions will last approximately 60 minutes and will be facilitated by a gynaecology nurse specialist. Group rules will be set at the start, and each session will end with a short debrief, and mood self-rating in the accompanying guided workbook provided to patients. Participants will be given a workbook to support their attendance on the course and a separate reflective diary where they can document their thoughts, experiences and feedback of the different modules. The diary will be returned to the research team at the end of the course; however, the participants will be able to keep the course workbook.

SPONSOR REFERENCE: 1097

OurPERSPECTIVE endometrial cancer survivorship Study

Protocol Version v1.0 14/10/2025

IRAS: 363748

Focus Group

Within 4 weeks of course completion, participants will be invited to take part in a virtual focus group to provide qualitative feedback on their experience, the data collection from each participant will conclude at 3-months. Discussions will explore perceived benefits, challenges, and suggestions for improvement. Sessions will be audio recorded, transcribed, and anonymised for analysis. The number of participants in each focus group will be 4-6 in order give participants time and opportunity to share their experiences. For individuals who do not wish to discuss their experiences openly, the option of a one-one virtual or telephone interview with the research fellow will be offered.

Withdrawal or Early Exit

If a participant withdraws before completing the course, the reason (if provided) will be recorded. Participants will be asked if they are willing to complete an early-exit telephone interview in order to explore their reasons and what could be done to improve the course to reduce future withdrawals.

Mode of Delivery

All questionnaires will be completed remotely (online or postal). The OurPERSPECTIVE intervention and focus groups will be delivered virtually (videoconferencing platform). No face-to-face study visits are required.

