5.5 Study intervention(s) and comparator(s)

5.5.1 Description of study intervention

The study intervention is OurPERSPECTIVE, a virtual, group-based survivorship course co-designed with women who have experienced endometrial cancer.

SPONSOR REFERENCE: 1097

OurPERSPECTIVE endometrial cancer survivorship Study

Protocol Version v1.0 14/10/2025

IRAS: 363748

The course will be facilitated by a gynaecology clinical nurse specialist who is part of the UHL direct clinical care team and will be known to the participants. The course will be delivered online via a secure videoconferencing platform (Microsoft Teams). The course will run for 6-8 consecutive weeks, with one session each week lasting approximately 60 minutes. There are 6 core modules for all participants and 2 additional modules (menopause and sexual function) that participants can chose to attend if they wish. Each session combines education, discussion, workbook activities and peer support, and covers the following modules: physical activity, sleep disturbance, body changes, tiredness, fear of recurrence, tiredness, menopause, and sexual disturbance.

At the start of the course, group rules will be established to create a safe and respectful environment. Each session will conclude with a short debrief to check wellbeing and provide closure. The specialist nurse who will be facilitating the course will be able to provide additional support to participants who become distressed or indicate that they need additional support during a session.

Attendance at each session will be recorded in the attendance log. The courses will aim to have 10 women per cohort, with 3 cohorts planned for the feasibility study.

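### Retention is tied to completing an 8-week course, but the course is also described as 6-8 weeks with two optional modules, and completion is never defined

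*Protocol*

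**What the plan says.** The Study Summary and the objectives table in section 2 both define the measure as "Retention rates (proportion of participants completing the 8-week course". Section 8.3.2 carries this into the analysis as "the proportion completing the 8-week programme". Section 1 also calls the intervention an 8-week course, and section 5.4 plans for eight: "Attendance at each of the 8 weekly online group sessions will be recorded in the case report form".

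Section 5.5.1 describes the course differently: "The course will run for 6-8 consecutive weeks, with one session each week lasting approximately 60 minutes". It sets out "6 core modules for all participants and 2 additional modules (menopause and sexual function) that participants can chose to attend".

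The attendance item that follows retention in section 8.3.2 does distinguish six core from two optional sessions. Section 8.7 lists three analysis sets (Enrolled, Intervention, Feasibility) but assigns none of them to retention. No section states what a woman must do to have completed the course.

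**The concern.** The wording of a primary measure does not fit the intervention it measures. A woman who attends all six core modules and declines the other two has done everything section 5.5.1 asks of her. Whether she counts as retained depends on how the 8-week phrase is read. If all eight sessions are needed, she is grouped with women who dropped out.

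Retention is primary wherever the primary outcome is set out, and in section 2 it is one of only two primary measures. The Study Summary says the primary measures will determine whether a full randomised trial is justified. No hypothesis test is planned, so the reported percentage is itself the result. If the reading is settled after the attendance data are seen, the headline figure could move a long way with no change in what the women did.

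There is a knock-on effect in section 8.4, which examines feasibility outcomes by menopause status among other characteristics. One of the optional modules is on menopause. On an all-eight reading, a difference in retention by menopause status could simply reflect who found that module relevant.

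**Working it through.** **Inputs from the protocol**

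- Sample size: about 30 (section 8.1). Section 5.5.1 plans 3 cohorts of 10, and 3 × 10 = 30, so the two agree.
- Modules: 6 core + 2 optional = 8 (sections 5.5.1 and 8.3.2).
- Course length: 8 weeks (Study Summary, sections 1, 2, 5.4 and 8.3.2), or 6 to 8 weeks (section 5.5.1).
- Retention target, expected completion and expected optional uptake: none given.

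**Step 1. One woman under three readings.** Take a woman who attends all six core sessions and neither optional one.

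| Reading of completing | Her status |
|---|---|
| All six core sessions | Completer |
| All eight sessions | Non-completer |
| Still taking part at week 8 | Not determinable; depends on when the optional modules fall, which the text does not say |

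The text does not choose between these readings.

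**Step 2. Effect of one woman.** 1/30 = 3.3 percentage points.

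**Step 3. Effect across the group.** Let c be the share of enrolled women completing all six core sessions, and u the share of those women who also take both optional modules. Then

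- core-based rate = c
- all-eight rate = c × u
- gap = c × (1 − u)

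Both c and u are assumptions.

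With c = 27/30 = 90%:

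| Uptake u | All-eight rate | Core-based rate | Gap |
|---|---|---|---|
| 30% | 0.9 × 0.3 = 27% | 90% | 63 points |
| 50% | 0.9 × 0.5 = 45% | 90% | 45 points |
| 70% | 0.9 × 0.7 = 63% | 90% | 27 points |
| 100% | 0.9 × 1.0 = 90% | 90% | 0 |

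At u = 50% the count is 27 × 0.5 = 13.5, that is 13 or 14 women (43% or 47%).

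With c = 30/30 = 100%, the all-eight rate is 24/30 = 80% at u = 80%, 15/30 = 50% at u = 50%, and 6/30 = 20% at u = 20%. The core-based rate stays at 100%.

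**Step 4. Comparison with sampling error.** The exact (Clopper-Pearson) 95% interval for 27/30 is 73.5% to 97.9%, and for 14/30 it is 28.3% to 65.7%. At half uptake, then, the choice of definition moves the estimate outside the sampling uncertainty of the core-based figure. At high uptake the difference shrinks, and at full uptake it vanishes.

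**The case against.** The strongest reply is that no section requires eight sessions. The texts can be made to agree: the timetable is eight weeks, each woman's own attendance spans six to eight depending on her choices, and completing means doing what the course asks of her. On that reading nobody is misclassified. This stands to the extent that misclassification is possible but not certain. A reader might infer that the protocol already scores women who skip the optional modules as failures. It sets no such rule, and no retention threshold against which anything could fail. But the benign reading is not written down either.

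Second, section 8.3.2 reports attendance across core and optional sessions next to retention, so a reader of the results could see why a low rate arose. That is a real mitigation, though it leaves the retention numerator undefined. It also rules out the inference that six of six core sessions would be reported as 75% attendance: no attendance rate out of eight is planned.

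Third, a separate analysis plan may supply an operational rule for completion. It may, and a session threshold alone could be left to it. The conflict between the protocol's descriptions of the course lies in the protocol itself and has to be settled there.

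Fourth, section 5.5.1 lists tiredness twice, and a reader might conclude that only five core modules exist. That is not supported. Six core modules are stated in both sections 5.5.1 and 8.3.2, the repetition is probably a slip, and the figure summarising module content is not available here.

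Finally, the completion and uptake rates used above have no source in the protocol. That is correct, and they serve only as illustration.

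**Conclusion.** The point holds as an inconsistency in course length combined with an undefined completion rule for a primary measure. On the literal 8-week reading, retention would count a permitted choice as dropout, at 3.3 points per woman with 30 enrolled. The illustrative gap of 45% against 90% rests on two assumptions, 27 of 30 completing the core and half of those taking both optional modules. The gap could be anything from zero at full uptake to the whole of the core rate at no uptake.

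This should be fixed before enrolment, because the measure informs the decision on a full trial. It does not undermine the study. The analysis is descriptive, and attendance at each session is recorded, so the rate can be computed under any session-based definition from the same data. What is missing is a prior commitment to one of them.

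**What to change.** 1. Reconcile the course length across the Study Summary and sections 1, 2, 5.4, 5.5.1 and 8.3.2. Which description is right is for the sponsor to decide.
2. In sections 2 and 8.3.2, define completion by attendance at the six core sessions only, with a stated minimum number chosen by the sponsor before enrolment. Optional-module uptake then does not enter retention.
3. Name the Enrolled set of section 8.7 as the denominator.
4. Keep the attendance summary for core and optional sessions already planned in section 8.3.2. Record in section 5.4 which sessions are core and which are optional.

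The cost is wording only. No new data are needed, since sections 5.4 and 5.5.1 already provide for logging attendance at each session.
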